3.1 Funding

This project is an investigator-lead, internally funded study, supported by philanthropic funds.

3.2 Project Resources and Context

The study will be conducted in the PTSD Research Clinic at the TI/NPRC. All needed resources to conduct the study are provided within the Institute. The Clinic is a research facility offering treatments at no cost in exchange for participation in leading edge research. This clinic is designed to help us to uncover the best ways of treating TSR conditions like PTSD as well as help us understand how to reduce the incidence of comorbid conditions.

This research study is the first project run out of the PTSD Research Clinic, marking the beginning of a larger research program dedicated to exploring emerging treatments for PTSD and other trauma-related conditions. The clinic will soon be offering multiple research studies aimed at understanding and improving treatment options for individuals affected by stress and trauma. Potential participants will be carefully triaged into the most suitable clinical pathway following a comprehensive assessment to ensure they receive the best support and intervention. For those not eligible for the studies, appropriate referrals will be made to local clinical services to ensure continuity of care and access to alternative treatment options.

4. Background

4.1 Impact of Trauma

The global prevalence of trauma exposure is high, with research consistently indicating that a significant majority of individuals have experienced trauma in their lifetime (Douglas et al., 2023). The World Health Organisation found that 70.4% of adults had experienced at least one traumatic event in their life ($N = 70,000$, 24 countries) (Kessler et al., 2017). The now infamous Kaiser Permanente's and Centre for Disease Control's Adverse Childhood Experiences study found that 64% of people had experienced at least one adverse event and 12% had experienced four or more before 18 years old (Felitti et al., 1998). More recently, the Australian Child Maltreatment Study found that many Australians have experienced child maltreatment, including physical (32%), sexual (28.5%), and emotional (30.9%) abuse and exposure to domestic violence (39.6%) (Matthews et al., 2023).

Cumulative trauma can exhaust the body's stress response, damage developing brains' functions and structures, and lead to performance deficits across multiple areas including: behavioural and emotional dysregulation, learning, attention, and language use, difficulty navigating relationships, poor decision making, and dysfunction in fear extinction (Evans & Coccoma, 2014, Kisiel et al., 2014, Sheridan et al., 2020, Van der Kolk et al., 2005). The extensive body of evidence documenting the adverse effects of trauma on childhood development and its lingering impact on our physical and psychological health as adults has been a catalyst for significant advances in how we support individuals who have experienced a traumatic event. It has also deepened our understanding of a major psychological consequence that can emerge from such experiences: PTSD.

Post-Traumatic Stress Disorder (PTSD)

PTSD is a possible outcome of exposure to a traumatic event. Individuals who have a PTSD diagnosis may recurrently experience memories, emotions, and sensations of a traumatic event through sensory nightmares or flashbacks, have difficulty sleeping, poor concentration, hypervigilance, irritability, emotional withdrawal and experience avoidance (Yehuda et al., 2015). PTSD related nightmares have been linked with a five-fold increase in suicidality and can be resistant to treatment (Sjostrom et al., 2007).

A wide variety of traumatic events can cause PTSD (Kessler et al., 2014; Yehuda, 2002), and the specific type of traumatic event can influence the course of the disorder (e.g., chronic vs non-chronic, immediate vs delayed onset) (Santiago et al., 2013; Smid et al., 2009). Taking this into account, it has been estimated that 11% of

Australians will experience PTSD at some point in their life, with women being at almost twice the risk of men (14% and 8% respectively) (ABS, 2022).

Typical PTSD treatment may involve the use of pharmacotherapy, psychological therapy, or a combination of both. Clinical guidelines recommend sertraline, fluoxetine, paroxetine, and venlafaxine as pharmacologic treatments for PTSD, despite evidence demonstrating only marginal efficacy over placebo (Hamblen et al., 2019; Martin et al 2021; Hoskins et al; 2021).

Trauma-focused psychotherapies (TFPs) are among the most supported treatments for PTSD, demonstrating greater effect sizes compared to current pharmacological options (Mavranouzouli et al., 2020; Weber et al., 2021). TFPs are based on the premise that by facilitating emotional regulation while an individual is being exposed to their trauma memory will result in extinction learning, altering trauma related cognitions, and reducing avoidant behaviours. Prolonged Exposure (PE), Cognitive Processing Therapy (CPT), Trauma-focused Cognitive Behavioural Therapy (TF-CBT), and Eye Movement Desensitisation and Reprocessing (EMDR) are recommended treatments for adults while TF-CBT or EMDR are commonly suggested for children and adolescents (Hamblen et al., 2019; Martin et al., 2021, APA, 2017; NICE, 2018, Lewey et al., 2018, Lewis et al., 2020, McLean et al., 2022).

Whilst TFPs have shown the most robust effect sizes of all currently accepted PTSD treatments, treating PTSD in clinical practice remains fraught with difficulties. TFPs are usually delivered over 8-16 weeks (Watkins et al., 2018) by highly trained specialists. It is marked by high drop-out rates, high risk of relapse, treatment resistance, and significant residual symptoms (Tripp et al., 2020; Larsen et al., 2019; Smid et al., 2018; Niles et al., 2018; Green, 2013). Similarly, the modest outcomes of pharmacological treatments over placebo often do not justify the associated costs, impact of long-term use, and adverse side-effects individuals may experience. As a result, new approaches are needed to enhance treatment efficacy and provide lasting relief from trauma symptoms.

Memory Reconsolidation Blockade: An Emerging Trauma Treatment

The concept of memory reconsolidation blockade has been proposed as a potentially more effective method than extinction training (Nader & Hardt, 2009). A landmark study by Nader et al. (2000) showed that administering a protein synthesis inhibitor (anisomycin), following the reactivation of a fear memory could block (or impair) the reconsolidation of that memory in rodents. Subsequent studies in humans have shown that the reconsolidation of emotional memories can also be disrupted when specific pharmacological agents are used alongside the recall of traumatic events (Bergstrom et al., 2013, Parsons and Ressler, 2013, Ratano et al., 2014; Kindt et al., 2009).

The most used pharmacological agent in reconsolidation blockade research involving humans is propranolol. Propranolol is a lipophilic nonselective β -adrenergic receptor (β -AR) antagonist that crosses the blood-brain barrier, impacting the noradrenergic system and, putatively, the protein synthesis process (Przybylski et al., 1999; Cahill et al., 2000, O'Carroll et al., 1999). It has been widely employed in the treatment of conditions such as hypertension, ischemic heart disease, and arrhythmia (Srinivasan, 2019).

In preclinical studies, propranolol has consistently blocked the reconsolidation of fear memories across various tasks involving memory, including passive avoidance, contextual fear, and auditory fear conditioning (Debiec & Ledoux, 2004; Przybylski et al., 1999; Taherian et al., 2014). In humans, Cahill and colleagues (2000) demonstrated that, compared to a placebo, oral propranolol administered before viewing emotionally disturbing slides prevented the heightened emotional recall of those images. In patients, a randomised controlled trial by Brunet and colleagues (2018) found that oral propranolol was associated with reduced PTSD symptoms after six sessions, during which patients recalled a traumatic event 90 minutes after taking propranolol. Furthermore, propranolol has been shown to disrupt fear memories in healthy individuals (e.g., Kindt et al., 2009). It has also led to significant improvements in PTSD, anxiety and depression symptoms by the end of treatment in children exposed to war-related trauma in an open-label trial (Thierree et al., 2020).

Of four meta-analyses, two support reconsolidation impairment (Lonergan et al, 2013; Pigeon et al, 2022) and two others consider that the evidence is inconclusive (Raut et al., 2022; Steenen et al., 2022). Raut et al. (2022) meta-analysis examining oral propranolol interventions for disrupting trauma memories in PTSD patients reviewed seven studies reporting PTSD symptom changes and three studies assessing propranolol's effects on physiological responses. Interestingly, the findings indicated that propranolol did not significantly improve PTSD

symptoms, skin conductance, or electromyography responses, though it did reduce heart rate following trauma memory recall vs. placebo. However, there were methodological limitations across the studies, such as inconsistent propranolol dosages, variations in treatment session protocols, small sample sizes, and heterogeneity in effect sizes (Raut et al., 2022). This suggests that there are probably boundary conditions (some that have yet to be discovered) governing the use of reconsolidation impairment as a therapeutic modality. As a result, the authors recommended interpreting these findings with caution and called for more research on the topic.

Given the immense and growing burden of TSR conditions, which poses a significant crisis for individuals and public health systems, current therapeutic options alone are insufficient to address the problem. While the efficacy of propranolol-based reconsolidation blockade for patients remains under debate, the model is based on a strong animal model and emerging evidence suggests that it holds significant promise as a clinical treatment for TSR disorders, opening the door to therapeutic innovation. This potential lies in the unique attributes of reconsolidation blockade, which, unlike traditional PTSD treatments, offers the possibility of shorter therapist training, shorter treatment durations, low cost, good treatment acceptability, reduced adverse side effects, and reduced reliance on intensive clinical expertise. Thus, this research proposal aims to build on the existing literature to further investigate the usefulness of reconsolidation blockade as a therapeutic modality. By exploring this approach, we seek to expand on the potential benefits of targeting memory reconsolidation as a means of providing more effective and accessible treatment for individuals suffering from TSR disorders.

4.2 Aims

Primary aim: To determine if a 6-session course of reconsolidation blockade (i.e., oral propranolol treatment combined with script-driven trauma recall) is efficacious in reducing PTSD symptom frequency and severity in adults.

Exploratory aims: To examine the psychosocial, neurocognitive, neurobiological, neuroimaging and physiological effects of reconsolidation blockade treatment in adult participants with PTSD.

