4.3 Research Questions

1. Primary question: Will a 6-session reconsolidation blockade treatment be efficacious in reducing core PTSD symptoms frequency and severity.
2. Secondary question: Are there psycho-social, cognitive, and biological markers (genetic, circulating, and neural) that can predict treatment response to reconsolidation blockade treatment?

5. Project Design

	Screen	T1 Baseline Week 0	T2 Pre-treatment (after 4-week waitlist)	Intervention Weeks 1–6	T3 Post-treatment Week 7 or 8	T4 Follow up 1 1-month	T5 Follow up 2 3-month
Research Activity	30-min phone call	4-hour clinical assessment: Medical ax* Psycho-diagnostic ax Heart rate variability Substances screen Self-report measures - PDI - PDEQ - PCL-5 - IES-R - BDI-I - PTGI	4-hour clinical assessment: MRI CANTAB Biological ax Hair Clip Self-report measures -PCL-5 -IES-R -BDI-I - Any sig. changes from T1?	50-min RT session in week 1 Thereafter once weekly 25-minute RT sessions in weeks 2-6 Saliva IES-R	4-hour clinical assessment: MRI CANTAB Psych interview Biological ax Self-report measures - PCL-5 - IES-R - BDI-I - WHOQOL - PSQI	50-min clinical interview Self-report measures -PCL-5 -IES-R -BDI-I	4-hour clinical assessment: MRI CANTAB Psych interview Biological ax Hair clip Heart rate variability Substances screen Self-report measures -PCL-5 -IES-R -BDI-I -PTGI

		- ITQ - CTQ - WHOQOL - PSQI Eligibility met/not met					-WHOQOL - PSQI
Setting	Tele-health	UniSC	UniSC	UniSC	UniSC	Telehealth	UniSC
Participants	>18yro Diagnosed PTSD	>18yro Diagnosed PTSD	>18yro Diagnosed PTSD	>18yro Diagnosed PTSD	>18yro Diagnosed PTSD	>18yro Diagnosed PTSD	>18yro Diagnosed PTSD
Identifiability during data collection	Identifiable	Identifiable	Identifiable	Identifiable	Identifiable	Identifiable	Identifiable
Identifiability during data storage	Re-identifiable	Re-identifiable	Re-identifiable	Re-identifiable	Re-identifiable	Re-identifiable	Re-identifiable
Identifiability at the time of publications	Non-identifiable	Non-identifiable	Non-identifiable	Non-identifiable	Non-identifiable	Non-identifiable	Non-identifiable
Recruiting methods	-Social media -Flyers -Website -Email circulated to referral networks	n/a	n/a	n/a	n/a	n/a	Email/phone call to previous participants who consented to future contact
Consent	Verbal via survey question	Written Unspecified Written consent requested to contact for future projects	Verbal	Verbal	Verbal	Verbal	Verbal

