5.1 Methodological Approach

In this study, participants will receive manualised (Brunet & Lonergan, 2010) propranolol-based reconsolidation blockade treatment (hereafter called RT) once per week for six weeks in a single treatment arm. Each RT session will be conducted by trained practitioners. Session 1 will last 50 minutes while Sessions 2-6 will last 25 minutes and involve a script recall exercise to activate the specific trauma memory targeted for that session. Participants will be instructed to take the study oral medication (1mg/kg according to ideal weight) 60 minutes with a light snack before each scheduled RT session (i.e., 6 once-a-week doses over 6 weeks). The first dose will be taken on site under supervision of a registered nurse with access to a medical doctor. Subsequent doses will be taken at home before each treatment session. On the day of the first propranolol administration, the research trials

physician (GP) will be on-site to monitor for potential hypotensive events and ensure participant safety. This protocol builds on previous propranolol research and aligns with memory reconsolidation theory principles.

Throughout the study, participants will remain under the care of their existing treating team (i.e. medical practitioner, psychiatrist and/or psychologist), who will oversee any modifications to their existing treatments. RT will be used as an adjunctive treatment, allowing participants to maintain their current psychotropic medications, if any, under their physician's guidance. Any changes in medication will be documented by the study staff. It will be strongly recommended to participants and their treating team to not commence any new mental health treatments during the clinical study.

The primary outcome of the study is a change in PTSD symptomatology, assessed using the battery of psychological assessments (i.e., PCL-5, structured clinical interview) at several time points:

- T1 Baseline assessment (week 0)
- T3 post-treatment assessment (week 7 or 8)
- T5 Follow-up 2 (3 month)

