5.2 Participants

Male and female adult participants aged 18 years and older, with a current diagnosis of non-complex PTSD, as assessed using the battery of tests within our psychological assessment protocol. The study will aim to recruit 150 participants. Investigators will keep a record of participants who were considered for the study but were not enrolled. This is done primarily to document the selection process, ensure transparency, and identify any potential selection biases. Please refer to section 5.3 for the process involved with the Participation Screening and Identification Log. Participants with a condition that may contraindicate the use of MRI will still be eligible to take part in the overall study. Only participants who meet all of the inclusion criteria and none of the exclusion criteria will be eligible to participate in the study.

Inclusion criteria:

- Persons aged 18 years +
- Participants must be able to understand Research Project Information Sheet (RPIS) and provide written informed consent on the Participant Informed Consent Form (PICF) (including both adequate intellectual capacity and fluency in English language)
- Diagnosis of PTSD
- Participants must undertake psychological, cognitive, and biological assessments, tolerate propranolol and not be taking any drugs that could contraindicate propranolol.
- Participants must have a current treating team who is managing their mental health diagnosis
- Persons of child-bearing potential must agree to use a *highly effective method of contraception

*Highly effective methods of contraception are listed below:

- o Hormonal methods of contraception including oral contraceptives containing combined estrogen and progesterone, a vaginal ring, injectable and implantable hormonal contraceptives, intrauterine hormone-releasing system (e.g. Mirena) and progestogen-only hormonal contraception associated with inhibition of ovulation o Nonhormonal intrauterine device (IUD)
- o Bilateral tubal occlusion
- o Vasectomised participant/partner with documented azoospermia 90 days after procedure, if that partner is the sole sexual partner.
- o Abstinence from heterosexual intercourse: when this is in line with the preferred and usual lifestyle of the participant.

Periodic abstinence (e.g., calendar, ovulation, post-ovulation methods) and withdrawal are not acceptable methods of contraception. Persons in the following categories are not considered persons of childbearing potential

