5.10 Data Management and analysis

Once completed, screening for the total number of completed surveys will take place and we will ensure no personal details (names, contact details etc) are associated with the survey information. All data collected will be stored in line with the UniSC Research Data Management Procedures.

A unique code will be generated for each participant enrolled in the study to de-identify data. The information for linking unique codes to participant contact information will be made accessible to necessary project staff for the purposes of scheduling assessments. All electronic data will be stored securely on computers at the TI/NPRC or on secure research specific databases. Only researchers will have access to the data and other research documents. The computers will be secured by usernames and passwords and protected from external access. Hard copy documents, material, and data will be kept in a locked filing cabinet, inside a locked office. All paper records will be securely converted to pdf files to mitigate the risk of data loss through an emergency (e.g. fire or flood).

Re-identifiable data (using the unique code identifiers) will be exported from Qualtrics to IBM SPSS for analysis. Statistical analyses will include generalised linear models (GLMs), analysis of the relative change index and frequentist statistics. A significance level of $p < .05$ (two-sided test) will be utilised where required. Data will be inspected for outliers and any spurious data will be corrected or removed prior to analysis. A detailed data analysis plan will be constructed by a statistician including the research questions and variables included. Missing data will be examined for missingness patterns. If the data is missing at random or completely at random, data imputation strategies may be employed in order to protect the integrity of this longitudinal sample and statistical power. Data will be analysed using descriptive, bivariate, and multivariate statistics using intent-to-treat analyses.

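### The primary aim asks whether reconsolidation treatment is efficacious, but a single arm measured from before an untreated waitlist can only estimate within-person change

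*Protocol*

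**What the plan says.** The primary aim in Protocol Section 4.2 is "To determine if a 6-session course of reconsolidation blockade (i.e., oral propranolol treatment combined with script-driven trauma recall) is efficacious" in reducing the frequency and severity of PTSD symptoms in adults. Section 4.3 repeats this as the primary question: "Will a 6-session reconsolidation blockade treatment be efficacious in reducing core PTSD symptoms frequency and severity".

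Section 5.1 fixes the design. RT is given "once per week for six weeks in a single treatment arm", as an adjunct to whatever psychotropic medication and care the participant already has. No placebo, recall-only or concurrent untreated group is described. The same section states "The primary outcome of the study is a change in PTSD symptomatology", assessed by PCL-5 and structured clinical interview, and lists T1, T3 and T5. T2 is not listed.

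The table in Section 5 and the text of Section 5.4 describe a 4-week waitlist between T1 and treatment. The table schedules PCL-5, IES-R and BDI-I at T2, after that waitlist.

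On sample size, Section 5.2 says only "The study will aim to recruit 150 participants". On testing, Section 5.10 names p < .05 ("two-sided test) will be utilised where required") and leaves detail to a data analysis plan to be written by a statistician.

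The secondary question in Section 4.3 asks about psychosocial, cognitive and biological markers "that can predict treatment response to reconsolidation blockade treatment". Section 4.2 has no secondary aim. Its other entry reads "Exploratory aims: To examine the psychosocial, neurocognitive, neurobiological, neuroimaging and physiological effects" of the treatment, which concerns effects on such measures rather than prediction from them.

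**The concern.** Asking whether a treatment is efficacious is a causal question. In this design everyone receives the drug, the scripted recall, therapist contact and usual care together. Symptom change over the period can also come from natural course, regression to the mean in people who entered because they were symptomatic, expectancy, or care received elsewhere. Nothing in the primary comparison separates these from RT.

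Starting the clock at T1 makes this worse than it need be, because part of the measured change occurs before the first dose.

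The stakes are in the conclusion. Section 4.1 itself describes the efficacy of propranolol-based blockade as still debated and cites meta-analyses on both sides. Section 6 foresees journal publication, wide media interest and sharing with clinical organisations. A significant pre-post fall reported as efficacy would claim more than the trial can show.

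**Working it through.** **1. How much of the primary interval is untreated.** The table in Section 5 places T2 after a 4-week waitlist, treatment in weeks 1 to 6, and T3 in week 7 or 8. A 4-week wait cannot fit before week 1 if T1 is week 0, so I assume that the week count restarts at treatment.

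- T1 to T2: 4 weeks.
- T2 to T3: about 7 to 8 weeks.
- T1 to T3: 4 + 7 = 11 to 4 + 8 = 12 weeks.
- Untreated share: 4/12 = 33% to 4/11 = 36%.

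Roughly a third of the T1-to-T3 interval precedes treatment. The T1-to-T5 change contains the same 4 weeks.

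**2. What a significant pre-post test would mean.** The protocol gives no effect size, SD, power or dropout for the target of 150, so there is no figure of its own to reproduce. Inputs:

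- n = 150 (Section 5.2), all assumed complete.
- Two-sided 0.05 (Section 5.10).
- dz = mean untreated change divided by the SD of change. This is an assumption, shown over a range.

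With no effect of RT, the probability of a significant fall is Φ(dz × √n − 1.96), and √150 = 12.247.

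| Untreated dz | dz × √150 − 1.96 | Probability, n = 150 | Probability, n = 105 |
|---|---|---|---|
| 0.1 | 1.225 − 1.96 = −0.735 | 0.23 | 0.18 |
| 0.2 | 2.449 − 1.96 = 0.489 | 0.69 | 0.54 |
| 0.3 | 3.674 − 1.96 = 1.714 | 0.96 | 0.87 |

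The last column assumes 30% loss (150 × 0.70 = 105).

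If there were neither untreated change nor an RT effect, a significant fall would occur 2.5% of the time. The excess over 2.5% comes wholly from change that has nothing to do with RT.

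**3. What T2 offers.** PCL-5 is already collected at T1, T2 and T3, so two within-person changes are available: T1 to T2 (waitlist) and T2 to T3 (treatment period). The contrast is limited in four ways:

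- The intervals differ (4 weeks against about 7 to 8).
- The waitlist always comes first, so regression to the mean after entry falls mainly there.
- Order is not randomised.
- Both changes use the T2 score, with opposite sign. Anything that shifts T2 scores moves one change up and the other down.

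**4. The marker question.** In one arm, a marker can be related to change during RT. Whether it would relate equally to change without RT is not observed. An association is therefore open to both a prognostic and a treatment-specific reading. Sections 4.2 and 4.3 also differ in status (exploratory against secondary) and in content (effects on measures against prediction from them).

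**The case against.** The strongest reply has three parts.

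First, Section 4.2 defines the treatment as propranolol combined with recall, so the aim concerns the package and does not claim to isolate the drug. That stands, and it removes part of the drug-versus-recall objection. It does not help with time, expectancy, usual care or regression to the mean, which confound the package as a whole.

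Second, the protocol does contain an internal control, the waitlist with repeat PCL-5. That is true, but Section 5.1 leaves T2 out of the primary outcome and no waitlist comparison is stated.

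Third, people often say that a marker predicts response when they mean only that it identifies who improves, and one arm can find that. This is fair. The question needs rewording, not removal.

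A reader might also infer stronger points that the documents do not support:

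- **That a significant result is near certain whatever its cause.** The table above shows 0.23 at dz = 0.1, and the protocol gives no value for untreated change.
- **That the lack of error control for markers is a protocol error.** Section 5.10 applies its significance level only where required, states no number of marker tests, and defers detail to an analysis plan that is not at hand.
- **That the outcome is purely self-report.** Section 5.1 also names a structured interview.
- **That relating every marker to T1-to-T2 change would settle its prognostic status.** MRI, CANTAB, blood and hair are first taken at T2, so for those markers the check would look backwards.

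**Conclusion.** The point holds for the wording of the primary aim and question and for the choice of primary time points. A single-arm T1-to-T3 or T1-to-T5 change cannot support a conclusion that RT is efficacious. About a third of the T1-to-T3 interval is untreated, given the reading of the week count above. The probabilities of 0.23, 0.69 and 0.96 illustrate how modest untreated change could produce a significant result. They rest on an assumed dz, 150 complete cases and a normal approximation, and are not forecasts for this trial.

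The study remains worthwhile as an estimate of change during RT. The marker point is smaller: its label and wording need to match Section 4.2 and what one arm can show.

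**What to change.** 1. In Sections 4.2 and 4.3, restate the primary aim, question and planned conclusion as estimating within-person change in PTSD symptoms during RT. Say that no efficacy attribution to propranolol or reconsolidation blockade will be made.
2. In Section 5.1, add T2 as a primary time point and use T2 PCL-5 as the pre-treatment reference. Report T1-to-T2 change beside T2-to-T3 change, each with a confidence interval.
3. State that the waitlist is only a partial control: shorter than the treatment period, always first, unrandomised, and sharing the T2 score. Settle whether T2 falls at the end of the waitlist (table in Section 5) or during it (Section 5.4), since this sets the length of the comparison.
4. The table lists no interview at T2. Say that the T2 reference applies to PCL-5 and that interview-based change still runs from T1.
5. Reword question 2 as exploratory, concerning markers associated with change during RT, in line with Section 4.2.

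No new data collection is needed. The cost is a more modest headline claim, some redrafting and slightly more analysis.
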